Christiana Care Hospital
Neurology Department

Study Protocol

Enhancement of Behavioral and Cognitive Outcomes in Autism Spectrum Disorder Via Neurostimulation

NCT05371912

Date: 7/21/2021

AIMS:

Aim 1: To determine the effects of High frequency (HF) repetitive Transcranial Magnetic Stimulation (rTMS) of the inferior parietal lobule (IPL) on social/behavior deficits in children and young adults with ASD.

Aim 2: To assess the differential effects of HF rTMS of the left versus right IPL on linguistic and visual coding abilities in ASD.

Aim 3: To evaluate the effects of right/left HF rTMS stimulation of IPL on executive functioning in ASD.

BACKGROUND:

ASD encompasses a wide range of impairments in the reciprocal social and communicative skills as well as presence of restrictive and/or repetitive patterns of behaviors. The environmental, genetic, and biological etiologies for ASD are yet to be fully defined. ASD is heterogeneous in nature and thus far, numerous genetic factors have been identified in the affected children, including single gene mutations, chromosomal abnormalities, and sub-microscopic deletions or duplications, altogether accounting for approximately 10% of cases. Some authors have predicted between 350 to 400 ASD susceptibility genes. Copy number variations are also found to play an important role in developing the ASD phenotype. Abnormalities in genes involved in epigenetic regulation, including mRNA translation, have been reported in ASD. Far less progress has been made in ascertaining the contribution of environmental factors in ASD.

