Language, the most treasured attribute of humans, is often impaired in ASD. Stimulation of left frontal lobe has been known to improve verbal fluency in children with ASD (14). While formulating language is modulated by the left posterior frontal lobe, deciphering language is localized to the left anterior temporal lobe. As such, the mirror neurons and language centers grossly colocalize in the same regions on the left hemispheres.

Moreover, these children experience issues with attention, self-regulation, and impulse control (ADHD), all attributable to abnormalities in frontal lobe connections. Stimulation of the frontal lobe has been reported to improve attention in individuals with ADHD. There are but 2 published studies on the application of rTMS in ADHD. High-frequency stimulation of the right dorsolateral prefrontal cortex resulted in an improvement in attention (1, 2).

While in right-handed individuals the left hemisphere is solely responsible for language function, in left-handed people, bilateral representation of language function is not uncommon. Right hemispheric language dominance is extremely rare. As such, for all practical purposes, the left hemisphere is considered the dominant hemisphere for language. On the other hand, the right hemisphere modulates visual and spatial processing and reasoning.

METHODS:

This is a prospective, double blind study to examine the impact of rTMS on social behavior and cognitive outcome measures in children and young adults with ASD.

The patients followed in our neurology clinic who meet the DSM-V criteria for ASD will be given the opportunity to join this study. The diagnosis of ASD will be confirmed with the Gilliam Asperger Disorder Scale (GADS) which is a standardized questionnaire and used routinely for this purpose.

Depending upon the underlying symptoms, the patient may be receiving various drugs such as stimulants or other medications for behavioral control. We will make every effort to minimize use of medications during the period of the study. If possible, the unnecessary pre-existing medications will be tapered off. Moreover, unless the child is experiencing dangerous impulsive behavior, no new medications will be introduced during the period of the study.

INCLUSION CRITERIA:

1. Fulfilling the DSM-V criteria for ASD
2. Diagnosis of ASD confirmed by GADS
3. The patient exhibiting adequate understanding and cooperation for the procedure

EXCLUSION CRITERIA:

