1. Children with ASD exhibiting significant anxiety or contact avoidance, precluding them from cooperating with the procedure
2. Children with a known diagnosis of seizures

INTERVENTION:

The rTMS treatment sessions will be scheduled 2 days a week for 5 weeks. In the beginning of each session, a single pulse stimulation will be utilized to determine the motor threshold. This is accomplished by increasing the intensity of the stimulation to achieve a twitch in the thenar muscle on the right hand. Eighty percent of the motor threshold will be applied for the treatment session. Each treatment session will consist of 10 minutes of HF rTMS delivery to the IPL, either the right or the left side, according to the paradigm detailed in the table below.

Frequency	10 Hz
Burst duration	10 seconds
Inter-burst intervals	20 seconds
Session time	10 minutes
Total stimulations per session	2000
Intensity	80% of motor threshold

The rTMS paradigm

rTMS TARGETING OF THE IPL:

For targeting the IPL, we are planning to use the standard 10/20 electrode placement system used for EEG recording. The IPL localizes to the Brodmann areas 7 and 40 and the P3/4 electrodes (15). A recent publication by Huang et al used sophisticated analysis of functional MRI and resting state functional connectivity in ASD and proposed multiple potential targets for neurostimulation including DLPFC, angular

gyrus and inferior frontal gyrus. Angular gyrus falls under Brodmann 40 and P3/4 EEG electric placement and overlaps with our proposed targeting of the IPL (16).

TREATMENT GROUPS AND THE EXPERIMENTAL DESIGN:

The patients will be randomized at the time of recruitment to either receiving left or right IPL stimulation. A standard shamming technique will be utilized to blind the patient regarding the treatment targeting (17). The neuropsychologist obtaining and interpreting the outcome measures will also be blinded. Only the clinician delivering the rTMS treatment will have a knowledge about the treatment targeting.

OUTCOME MEASURES:

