SRS-2: The Social Responsiveness Scale – Second Edition (SRS-2) is a 65-item, parent/caregiver-rated scale assessing social interaction and communication deficits (21). Different versions of the scale are used based on patient’s age and will be administered to parents. The total scale, which is the sum of responses (rated 1 to 4), is reported here. Raw scores range from 65 to 260 and are converted to t-scores (mean of 50 and standard deviation of 10). As such, higher scores suggest worse symptoms.

RRBs: Repetitive Behavior Scale-Revised is a parent rating scale that measures restricted repetitive behaviors (22). This scale consists of 43 items that correspond to six RRB subscales: stereotyped, self-injurious, compulsive, ritualistic, sameness, and restricted. Subscale scores are calculated by summing ratings (0=behavior does not occur to 3=behavior is a severe problem) of all correspondent items, representing the severity of each type of RRB. An overall RRB score is calculated by summing the subscale scores.

D-KEFS Verbal Fluency: The Delis-Kaplan Executive Function System (D-KEFS) Verbal Fluency task is composed of three subtests 2 of which will be implemented to quantify verbal fluency: Letter Fluency, Category Fluency, and Category-Switching Fluency (23). These subsets assess speed of generating words beginning with specified letters (Letter Fluency) or words from different categories (Category Fluency).

The final subtest evaluates cognitive set-shifting (an executive function) and verbal fluency. This test has alternate forms and is normed on individuals 8 years old through adulthood. Higher scores indicate more fluent word production.

WRAML-3: Design Learning subtest from Wide Range Assessment of Memory and Learning-Third Edition is a paper-and-pencil test with six subtests assessing immediate memory recall for participants aged 5-89 years (24). For this study, the Design Learning subtest will be used to assess immediate visual memory. In this task, the participant is shown a single card across four trials. The card has 18 different geometric shapes distributed across four quadrants. It is exposed for 10 seconds and then removed; after a 10 second delay the participant is asked to recall and draw the shapes in the correct locations. This procedure is repeated three times for a total of four trials.

NUMBER OF SUBJECTS:

This is a small pilot study which will include 20-30 subjects with ASD.

DURATION OF THE STUDY:

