We aim to recruit the subjects over a 2-year period. Each subject will receive the rTMS treatments 2 days a week for a period of 5 weeks and will be followed for three months after the intervention.

GENDER OF SUBJECTS:

There will be no gender preference when enrolling for this study.

AGE OF SUBJECTS:

We aim to recruit children and young adults with ASD. The subjects will be children 8 years or older and young adults up to 25 years old.

RACE & ETHNIC ORIGIN:

There will be no restrictions in enrollment based upon race or ethnic origin.

DATA ANALYSIS:

The numerical values generated by the above semi-quantitative measures (SRS, RRBs, NIHTB, DKEFS, WRAML-3) before and after treatment and after 3-moth follow up will be entered into an excel database and used for statistical analysis. For establishing statistical significance between the mean values before and after treatment, student t-test and confidence intervals will be used.

RISKS:

rTMS is a noninvasive method and not associated with any risks.

ADVERSE EVENTS:

The adverse effects of rTMS are mild and benign and consistent of transient headaches or scalp discomfort. Occurrence of seizures is quite rare; Krishnan et al. reported a total of 2 cases of seizures in 332 subjects participating in 35 trials of rTMS between 2004 and 2014. Both patients did have clear risk factors for seizures. These seizures occurred with the high-frequency stimulation of 15-20 Hz and short inter burst intervals which will be avoided in our protocol. Our study protocol will exclude all patients with history of epilepsy. Medications which may lower the seizure threshold will be avoided altogether if possible.

SEIZURE PROTOCOL:

If the patient should experience a seizure during the treatment, the following protocol will be followed

1. Universal seizure precautions and safety
2. Monitoring the vital signs

3. Calling the code and transferring the patient to the emergency room. If the seizure lasts for less than a minute, no specific treatments or interventions are necessary. However, the patient will be withdrawn from the study protocol. If the seizures are prolonged, in the emergency room, further decisions will be made regarding performing an EEG or other necessary treatments.

POTENTIAL BENEFITS TO THE SUBJECT AND SOCIETY:

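### Aim 2 compares left with right stimulation on language, but the plan neither provides for recording handedness, a likely modifier by its own account, nor uses it in the analysis

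*Combined protocol and SAP*

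**What the plan says.** AIMS states Aim 2 as follows: "To assess the differential effects of HF rTMS of the left versus right IPL on linguistic and visual coding abilities in ASD". The reason for expecting a side difference is given in the last paragraph of BACKGROUND. On right-handers it says: "While in right-handed individuals the left hemisphere is solely responsible for language function". On left-handers it says: "in left-handed people, bilateral representation of language function is not uncommon". It then calls language dominance of the right hemisphere very unusual and concludes: "As such, for all practical purposes, the left hemisphere is considered the dominant hemisphere for language".

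Handedness is not mentioned again:

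- **Eligibility.** The third and last item under INCLUSION CRITERIA is "The patient exhibiting adequate understanding and cooperation for the procedure". The two exclusions concern anxiety or contact avoidance, and seizures.
- **Allocation.** TREATMENT GROUPS AND THE EXPERIMENTAL DESIGN says: "The patients will be randomized at the time of recruitment to either receiving left or right IPL stimulation". It gives no ratio, blocking or stratification.
- **Test battery.** OUTCOME MEASURES lists cognitive tests and parent-rated scales. The only mention of a hand is the right thenar twitch under INTERVENTION, which sets the motor threshold and does not record handedness.
- **Analysis.** DATA ANALYSIS enters "The numerical values generated by the above semi-quantitative measures (SRS, RRBs, NIHTB, DKEFS, WRAML-3) before and after treatment" and at three months, and plans t-tests and confidence intervals for the change from before to after treatment. It names no covariate, subgroup or comparison between sides.

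On size, NUMBER OF SUBJECTS says: "This is a small pilot study which will include 20-30 subjects with ASD".

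**The concern.** The language half of Aim 2 depends on language sitting mainly on one side. The protocol names a group in which this is less reliable and then makes no use of that knowledge. The closing simplification does not settle the matter, because it leans on right-sided dominance being rare. The relevant case is bilateral representation. A subject with bilateral language can still count as left-dominant and yet show a smaller difference between left and right stimulation, and that difference is what Aim 2 seeks to estimate.

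What is at stake is mainly interpretation. If the trial finds no side difference on verbal fluency, or finds one, nobody could say whether left-handers contributed to it. POTENTIAL BENEFITS says that good results would lead to a larger study. The pilot could not then advise whether that study should restrict or stratify on handedness.

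**Working it through.** **Inputs from the documents.** Total sample 20-30 (NUMBER OF SUBJECTS) and two sides (TREATMENT GROUPS). The protocol states no significance level, power, effect size, SD, left-handed share or bilateral share, so there is no planned figure to reproduce.

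**Assumptions.** Equal arms (n = 10 or 15); two-sided 5% level; two-sample t-test. A share *h* = 10-20% of subjects are not right-handed. A share *b* = 15-100% of those show no left-right language difference, and everyone else shows the full difference.

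**Step 1: undiluted contrast.** Power comes from the noncentral t with 2n − 2 degrees of freedom and noncentrality d × √(n/2). The standardised difference detectable with 80% power is 1.325 at N = 20 and 1.060 at N = 30. For d = 0.8, power is 40% and 56%.

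**Step 2: dilution.** The retained effect is 1 − h × b. The table starts from a contrast with 80% power; the results agree for both sample sizes to the nearest percent.

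| h | b | Shrinkage h × b | Power |
|---|---|---|---|
| 10% | 15% | 1.5% | 79% |
| 10% | 30% | 3% | 78% |
| 10% | 50% | 5% | 76% |
| 10% | 100% | 10% | 71% |
| 20% | 15% | 3% | 78% |
| 20% | 30% | 6% | 75% |
| 20% | 50% | 10% | 71% |
| 20% | 100% | 20% | 61% |

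For d = 0.8, a 3% shrinkage takes power from 40% to 38% (N = 20) or from 56% to 54% (N = 30). A 10% shrinkage takes it to 33% or 48%.

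**Step 3: chance split of left-handers.** The number falling in one of two equal arms is hypergeometric.

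- 2 of 20: both in one arm, 47%.
- 4 of 20: 3:1 or worse, 58%; 4:0, 9%.
- 3 of 30: all in one arm, 22%. A 2:1 split is the best possible.
- 6 of 30: 4:2 or worse, 65%; 5:1 or worse, 17%.

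With an even number of left-handers, the 47%, 58% and 65% are simply the chances of anything other than an equal split.

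**Step 4: what such a split does.** Suppose language change differs by 0.5 SD between left- and right-handers (an assumption). A difference of two left-handers between arms of 10 moves the contrast by (2/10) × 0.5 = 0.10 SD. The standard error is √(2/10) = 0.45 SD.

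**Step 5: all subjects or right-handers only?** The signal-to-noise ratio is proportional to (1 − h × b) × √N for all subjects, and to √(N × (1 − h)) for right-handers only, ignoring the small change in degrees of freedom. They are equal when 1 − h × b = √(1 − h). At h = 10%, √0.90 = 0.949, so b = 0.051/0.10 = 51%. At h = 20%, √0.80 = 0.894, so b = 0.106/0.20 = 53%. Restricting the analysis gains power only if more than about half of the non-right-handed subjects show no side difference. This supports keeping everyone in the main contrast and using right-handers as a sensitivity analysis.

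**The case against.** The strongest reply is that the authors saw the issue and made a stated simplification, and that Aim 2 asks about people with ASD, not about right-handers with ASD. An average over everyone enrolled, left-handers included, is a legitimate answer to that question. This stands, and it is why all randomised subjects belong in the main contrast. It does not remove the need to know how far the average depends on a modifier that the protocol names.

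It can also be said that the point is second-order. DATA ANALYSIS specifies no left-versus-right test at all, and with 10-15 per arm even a difference of 0.8 SD has only 40-56% power. Both are larger weaknesses. They do not cancel this one, since any between-side analysis that is added will face the same question.

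A reader might infer several stronger things that the documents do not support:

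- *That the contrast is known to be diluted, or that left-handers often lack a side difference.* The protocol's wording is milder and gives no share. The 61% figure needs both assumed extremes at once, and b = 100% sits poorly with the protocol's view that the left can be treated as dominant.
- *That the omission cannot be repaired.* The protocol is silent on recording; it does not rule it out. Subjects attend a neurology clinic and are seen repeatedly, and handedness can be asked later. Only stratified allocation would be lost.
- *That an uneven split biases the result.* Randomisation keeps the contrast unbiased in expectation. Chance imbalance adds variability, which the standard error already reflects.
- *That adjusting for handedness would cure the problem.* A main-effect covariate does not address a side effect that differs by handedness.

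**Conclusion.** The concern holds in a limited form. The protocol makes handedness a plausible modifier of the Aim 2 language contrast but does not provide for recording it or using it in the analysis. The possible shrinkage runs from about 1.5% to 20%, and a hypothetical 80% power would fall to between 79% and 61%. This rests on assumed shares of non-right-handed subjects (10-20%) and of those without a side difference (15-100%), equal arms and a 5% two-sided test. None of these figures is in the documents, and the milder end costs very little.

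The case for acting therefore does not rest on a large loss of power or on bias. An uneven split is likely in a sample this small, and without the variable the result cannot be checked against the protocol's own caveat. The point concerns the language half of Aim 2 only; the protocol says nothing about handedness and visual function.

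**What to change.** 1. Add handedness to the baseline data, stating how it is obtained and what counts as right-handed.
2. Report handedness by arm.
3. In DATA ANALYSIS, specify the left-versus-right contrast for the language measure, keeping all randomised subjects as the main analysis. The before-and-after tests now planned do not supply it.
4. Prespecify the same contrast in right-handers only as a sensitivity analysis, to be read beside the main result and not in place of it.

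The cost is one baseline item and one extra analysis on a smaller sample. With 10-20% not right-handed, that is 20 − 2 = 18 to 20 − 4 = 16 subjects at N = 20, or 30 − 3 = 27 to 30 − 6 = 24 at N = 30.

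Stratified allocation and a handedness covariate are optional. With perhaps 2-6 subjects in the smaller stratum, blocks would mostly stay incomplete.

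### No rule places medication tapers before the baseline battery, so a later drug change would enter the before/after estimate for Aim 1, in a direction the documents do not settle

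*Combined protocol and SAP*

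**What the plan says.** METHODS acknowledges that at entry "the patient may be receiving various drugs such as stimulants or other medications for behavioral control". It then gives three instructions:

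- On overall drug use, the stated intention is: "We will make every effort to minimize use of medications during the period of the study".
- On drugs already being taken, the rule is: "If possible, the unnecessary pre-existing medications will be tapered off".
- On additions, the rule is: "unless the child is experiencing dangerous impulsive behavior, no new medications will be introduced during the period of the study".

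ADVERSE EVENTS adds that drugs lowering the seizure threshold are to be avoided where possible. Neither section gives a taper start or end, a washout, a stable-dose period, or an order relative to the baseline battery. INCLUSION CRITERIA and EXCLUSION CRITERIA do not mention medication. No study field for drug and dose is described, although clinic records may hold this.

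OUTCOME MEASURES places the battery at baseline, at the end of the rTMS course and three months later. On allocation, TREATMENT GROUPS AND THE EXPERIMENTAL DESIGN states: "The patients will be randomized at the time of recruitment to either receiving left or right IPL stimulation". INTERVENTION confirms that both sides are active: "Each treatment session will consist of 10 minutes of HF rTMS delivery to the IPL, either the right or the left side". The sham technique only hides the side. DATA ANALYSIS names one comparison, a t-test with confidence intervals on means before and after treatment, without adjustment for medication.

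Aim 1 is "To determine the effects of High frequency (HF) repetitive Transcranial Magnetic Stimulation (rTMS) of the inferior parietal lobule (IPL) on social/behavior deficits". Aim 3 is "To evaluate the effects of right/left HF rTMS stimulation of IPL on executive functioning in ASD".

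**The concern.** The protocol itself asks for drug reduction, so this is a planned co-intervention and not incidental drift. The drugs it names, stimulants and drugs for behavioral control, could plausibly affect what Aim 1 measures. A participant tested on a drug at baseline and off it at week 5 or at three months contributes a change that is not due to rTMS. With no arm free of active rTMS, nothing in the Aim 1 comparison removes it.

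Two limits apply. Aim 3 (Flanker, DCCS) is exposed only if it is read as a before/after question. A randomized left-versus-right contrast is balanced on average for drug changes, so the point does not extend to Aim 2.

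POTENTIAL BENEFITS TO THE SUBJECT AND SOCIETY makes a larger grant application depend on favorable results. A hidden benefit or an imitated one could each mislead that decision.

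**Working it through.** **No figure to reproduce.** NUMBER OF SUBJECTS gives 20-30 with no alpha, power, effect size, SD of change or dropout. DATA ANALYSIS does not say whether the t-test is paired or two-sided.

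**Inputs from the documents.** n = 20 or 30; SRS-2 T-scores have a normative SD of 10 and higher is worse (OUTCOME MEASURES).

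**Assumptions.** Paired test, two-sided 5%; pre/post correlation 0.7; true rTMS gain 0.5 SD, or none; share changing drugs after baseline p = 0.1, 0.3 or 0.5; shift per changer s = 0.2, 0.35 or 0.5 SD.

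**Step 1: mean bias.** If all shifts run one way, bias = p × s. The range is 0.1 × 0.2 = 0.02 SD to 0.5 × 0.5 = 0.25 SD. If the sample SD equals the normative 10, that is 0.2 to 2.5 SRS-2 points.

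**Step 2: noise.** SD of change without drug changes = √(2 × (1 − 0.7)) = 0.775 SD. Drug changes add p(1 − p)s² to the variance.

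**Step 3: power for a true 0.5 SD gain.** With no drug change, the noncentrality at n = 20 is 0.5/0.775 × √20 ≈ 2.89, and simulated power is 78.3% (n = 20) and 92.8% (n = 30). With p = 0.1, s = 0.2 and all worse, the mean is 0.48 and the variance 0.6 + 0.0036, so the noncentrality at n = 20 is about 2.76. Simulated power with all changers worsening (200,000 trials per cell), n = 20 / n = 30:

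| Share changing | 0.2 SD each | 0.35 SD each | 0.5 SD each |
|---|---|---|---|
| 10% | 74.6% / 90.5% | 71.5% / 88.2% | 67.5% / 85.5% |
| 30% | 66.6% / 84.9% | 56.6% / 75.5% | 45.2% / 63.3% |
| 50% | 58.4% / 77.4% | 41.2% / 58.1% | 25.5% / 36.9% |

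If two thirds worsen and one third improve, power is 71.1%-76.8% (n = 20) and 88.1%-91.9% (n = 30) at 0.2 SD, and 55.0%-73.6% and 74.1%-89.9% at 0.5 SD.

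**Step 4: no rTMS effect.** Two-sided rejection when all shifts run one way is 5.2%-8.4% (n = 20) and 5.3%-10.4% (n = 30) at 0.2 SD, and 5.9%-25.5% and 6.3%-36.9% at 0.5 SD. With mixed directions it stays at about 5%-8%. If the shift is a worsening, the excess rejections are apparent harm; if it is an improvement, they are false benefit.

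**Step 5: second method.** This uses the exact noncentral t in SRS-2 points, with an assumed true change of −5 and SD of change 7 or 10. If 30% change drugs and each worsens by 5 points, the shift is 0.3 × 5 = +1.5, so −5 appears as −3.5. The chance of detecting benefit falls from 86% to 56% (n = 20, SD 7), 97% to 75% (n = 30, SD 7), 56% to 32% (n = 20, SD 10) and 75% to 46% (n = 30, SD 10). With no rTMS effect, the same shift gives a false-worsening rate of 9%-21%. Reversed to −1.5, it gives a false-benefit rate of 9%-21%. The two methods agree on direction.

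**The case against.** The strongest reply is that this is an omission. The text is equally consistent with tapering at enrolment, and the seizure-threshold rule makes sense only if it is in force before the first session. A reader might infer that tapers will follow baseline; the documents allow that but do not say it. What stands against the reply is that METHODS sets the reduction within the study period, and a change between baseline and the first session still enters the change score.

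Second, every input to the size is assumed, only drugs judged unnecessary are tapered, and this is a pilot with no power target. That is correct. The 0.2 SD column is the more cautious reading, and nothing in the documents supports the corner with 50% changing by 0.5 SD in one direction.

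Third, a reader might infer that the main error is a hidden benefit, so the plan is merely conservative. The documents do not support this, because direction is unknown. Stopping an unneeded drug could improve scores. A drug started for dangerous impulsivity, which METHODS permits, could also improve them, so that exception is an exposure and not a safeguard. Nor is there a general ceiling on false benefit when withdrawal worsens scores: the rate approaches the nominal 2.5% as the shift shrinks. Practice, expectancy and regression to the mean also act on the same estimate, so this is one component of the error and not its net direction.

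Fourth, finishing tapers just before baseline could itself do harm. A temporary rebound captured at baseline would settle by week 5 and look like benefit. This stands, and the fix needs a settling period.

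**Conclusion.** The point holds as a preventable gap in design. The protocol directs drug reduction, does not place it before baseline, and tests Aim 1 with a comparison that cannot separate it from rTMS. The direction and size cannot be set from the documents. Under the cautious assumptions (10% changing, 0.2 SD each, all worse, correlation 0.7, paired two-sided 5% test), power for a true 0.5 SD gain falls only from about 78% to 75% (n = 20) or from 93% to 91% (n = 30). Losses are larger if more participants change or the shifts are bigger. The change is worth making because it is cheap and because, without a drug and dose record, study data could not show whether the problem was trivial or serious. Confidence is medium: the gap is plain in the text, but its effect is not known.

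**What to change.** 1. Complete any planned taper or seizure-threshold drug change, plus a stated stable-dose settling period chosen by the clinicians, before the baseline battery.
2. Randomize after that baseline, or as close to it as possible. Under the present rule of allocation at recruitment, a taper period would create randomized participants who may drop out with no baseline score.
3. Hold doses stable through the three-month visit unless a change is clinically needed.
4. Record drug and dose at all three assessments, and tabulate post-baseline stops and starts by arm.
5. Keep everyone in the main analysis, and label any unchanged-medication subset exploratory.

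The reason for item 5 is that a drug change may follow from the response to treatment. In a simulation with 30% changing and no drug effect, 40% of above-median and 20% of below-median responders were assumed to change. The unchanged subset (about 14 of 20, or 21 of 30) was then biased by −0.09 SD. With the shares reversed the bias was +0.09 SD, and false benefit under the null was 6.4% (n = 20) and 7.7% (n = 30), against a nominal 2.5%.

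The cost is a delayed baseline for participants who need a taper (their number is not given), one form field at three visits and one descriptive table. The change removes only the drug-change source. Practice, expectancy and regression to the mean remain, because no arm lacks active rTMS.
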